#### 8.7. Tumor Genomics

Full details of sample collection and handling of the sample will be described in the Lab Manual for the study.

For diagnostic purposes, a tumor biopsy at Pre-Screening is needed for EGFR assessment if there is no archived tumor tissue available. Samples could also be used for additional research such as (but not limited to) phenotypic assessments.

Optional biopsies may be taken at the discretion of the Investigator, following the patient's consent, for additional research at baseline (if sufficient archival tissue is not available) and during treatment. The biopsies may be used to confirm a radiological response/disease progression to inform treatment decisions and may also be utilized for analysis of immunological and other effects of the drugs on the tumor microenvironment.

## 8.9. Immunogenicity (Anti-Drug Antibodies)

All patients will have blood samples drawn to assess for ADA as described in Schedule of Pharmacokinetic, Pharmacodynamic, Immunogenicity, and Translational Assessments

Full details of sample collection and handling of ADA samples will be described in the Lab Manual.

#### 9. STATISTICAL CONSIDERATIONS

In general, summaries will be presented by cohort for both the dose escalation phase (Phase 1) and the expansion phase (Phase 2a) and will include the mean, standard deviation, standard error (where appropriate), median, minimum, and maximum values for continuous data; the median, 25th and 75th percentiles, minimum and maximum values (if estimable) for time-to-event endpoints; and the number and percentage of patients in each category for categorical data. Confidence intervals (CIs) may also be estimated for the mean (continuous data), median (time-to-event endpoints), or percentage of patients (categorical data). Baseline values will be defined as the last non-missing value before receipt of the first dose of study drug.

Listings of all individual patient data will be produced. A stand-alone Statistical Analysis Plan with mock Tables, Listings and Figures will be prepared.

#### 9.1. Population for Analyses

For the purposes of analysis, the following populations are defined:

The **safety analysis set (SAS)** will consist of all patients who received at least any amount of AFM24 or atezolizumab. The SAS set will be the primary population for all safety related endpoints except determination of the dose-DLT relationship.

The **full analysis set (FAS)** will consist of all patients who received at least any amount of both, AFM24 and atezolizumab. The FAS will be the primary population for all efficacy related endpoints.

The **dose-determining set (DDS)** will consist of all patients in the safety set, who have either (a) experienced DLT at any time during Cycle 1, or (b) met the minimum safety evaluation requirements without experiencing DLT within Cycle 1.

Additional details of DLT observation period and criteria to determine patients available for DLT are described in Section 4.2.3.1.

The DDS will be used in the escalation phase (3+3 design) to estimate the dose-DLT relationship.

The **PK** set consists of all patients who have received at least one adequately documented dose of AFM24 and have at least one adequately documented post dose PK measurement.

Patients who are screened and sign the informed consent but do not receive any treatment will be listed including reason for screening failure and any SAE that is related to study procedure. These patients will not be part of any summary table except for summarizing disposition.

#### 9.1. Sample Size Determination

## 9.1.1. Dose escalation phase (Phase 1)

A 3+3 dose finding design will be implemented. The number of patients dosed within each cohort is based on safety. The objective is to expose the lowest possible number of patients to the investigational drugs, while still being able to assess safety where the estimated MTD is the highest dose level with the observed toxicity rate less than 0.33.

Three to 6 patients will be enrolled in each cohort. If a DLT is observed in 1 of 3 patients, an additional 3 patients will be enrolled in that same dose cohort.

At least 6 patients must be treated at the MTD/RP2D (and a toxicity rate of less than 0.33 must be observed to be confirmed as the MTD).

Estimated number of patients: 18 patients (3 cohorts  $\times$  6 patients)

The sample size is based on the **DDS**, i.e., patients who are not evaluable for a DLT might be replaced. Thus, the actual number of patients may exceed 18, but will not exceed 28.

## 9.1.2. Expansion phase (Phase 2a)

An optimum Simon's two-stage design will be used (Simon 1989) for EXP-1 and EXP-2. EXP-3 and EXP-4 is exploratory with no hypothesis testing. The assumptions and sample size calculations for different cohorts are summarized in Section 9.4. Sample size estimation for EXP-3 and EXP-4 is provided in

## 9.2. Statistical Hypotheses

For phase 1, there will not be any hypotheses testing.

## 9.3. Statistical Analyses

The statistical analysis plan will be developed and finalized before database closes. This section is a summary of the planned statistical analyses of the primary and secondary endpoints.

#### 9.3.1. Safety Analyses

All safety analyses will be performed on the SAS, unless specified.

#### For primary endpoint of the escalation phase:

Occurrence of DLTs (see Section 4.2.3.1 for the definition). Patients in the DDS who experience a DLT will be presented in a summary table and listing by dose.

#### Other safety analyses (all phases):

Reported AE terms will be coded using the Medical Dictionary for Regulatory Activities (MedDRA) and summarized by preferred term and system organ class categories. Safety assessments will be summarized using descriptive statistics along with supportive listings. The number and percentage of TEAEs will be summarized by treatment group and overall, by system organ class, and preferred terms within each system organ class. Serious adverse events and AEs resulting in treatment discontinuation will also be summarized. Observed values and change from baseline in laboratory parameters, vital signs, and ECG parameters will be summarized by treatment group and study visit. Prior and concomitant medication use will be summarized by World Health Organization Drug Dictionary Anatomical Therapeutic Class code and treatment group.

All AEs meeting the DLT criteria will be summarized and listed for all patients throughout the study (in addition to the separate analysis of dose-determination using the DDS).

#### COVID-19 impacts:

Patients may be diagnosed with COVID-19 and experience SAEs associated with the disease that are not causally related to the investigational drug. However, it also is possible that an investigational drug might be causally related to a SAE associated with COVID-19 by making study patients more susceptible to complications from COVID-19. However, it is not possible to establish this potential causal relationship with a small number of SAEs reported in a clinical study. Descriptive statistics will be conducted to present SAEs by known and suspected COVID-19 infection and no infection. If possible, with the existing literature, the rates in the clinical study will be compared to reports in patients with similar comorbidities and levels of care. If the difference in SAEs compared to an external population suggests a causal relationship between the investigational product and the SAEs in study patients diagnosed with COVID-19, this finding will be submitted to FDA as an Investigational New Drug (IND) safety report in accordance with United States Title 21 Code of Federal Regulations (CFR) Part 312.32.

## 9.3.2. Efficacy Analyses

Objective Response: The number and percentage of patients achieving each category of response for OR (including CR and PR) will be provided. Results will be presented by percentages and 95% CI.

Clinical benefit rate (defined as CR or PR [any duration] OR SD ≥24 weeks): Results will be presented by percentages and 95% CI.

Disease control rate (DCR) at months 3, 6, 9, 12 and 15, as defined by achieving CR and/or PR and/or SD assessed by RECIST v1.1 will be presented by percentage rates and where appropriate the 95% CIs.

Progression-free survival will be measured from the date of the first dose of AFM24 and atezolizumab study drug to the date of disease progression or death from any cause, whichever occurs first.

Overall survival will be measured from the date of the first dose of AFM24 study drug to the date of death for any cause.

Duration of response will be measured from the date at which response criteria are met for CR or PR until the date of recurrence, PD, or death. Progression-free survival, overall survival, and DOR will be summarized using the Kaplan-Meier method. Censoring rules will be provided in the statistical analysis plan.

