# 4.2.2. Safety Lead-In Phase (for Both the Dose Escalation Phase [Phase 1] and the Expansion Phase [Phase 2a])

Seven days prior to Cycle 1 Day 1 (C1D1) (i.e., at Day -7), patients will receive a single dose of AFM24 (dose assigned to a given cohort) and will be observed for any AE for 1 week (from Day -7 through Day -1, the safety lead-in phase). Patients who have any Grade ≥3 cytokine release syndrome (CRS) or IRR symptoms lasting >6 hrs or any other possibly treatment-related Grade ≥3 non-hematological TEAEs or clinically significant hematological Grade ≥3 TEAEs during their

. Patient's eligibility criteria must be re-confirmed on or within 7 days before Day -7, before the administration of the first AFM24 infusion; please refer to inclusion and exclusion criteria sections (Sections 5.1 and 5.2, respectively) to see allowed time periods of screening assessments.

Patients not proceeding to combination therapy (AFM24 + atezolizumab) will be replaced.

Note: Patients are required to receive premedication approximately 1 hour before each dose of AFM24; a list of premedications is provided in Section 6.3.

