#### 8.3.2.2. Overall Survival

Overall survival (median) is determined by looking at the time from initial date of treatment to the date of death due to any cause. Survival data will be collected throughout the active treatment phase and during the long-term follow-up phase. Survival follow-up after patient discontinuation of investigational product will be conducted approximately every 12 weeks to assess for survival until patient death or withdrawal of consent.

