#### 8.3.2.3. Progression Free Survival (PFS)

Progression-free survival (median) is determined using the time measured from the initial date of treatment to the date of documented progression, or the date of death (in the absence of progression) of participants. Progression is defined using RECIST v1.1, as a 20% increase in the sum of the longest diameter of target lesions, or a measurable unequivocal increase in a non-target lesion, or the appearance of new lesion.

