#### 8.3.2.5. Clinical Benefit Rate

Clinical benefit rate is measured per RECIST v1.1 criteria as the proportion of patients who achieve overall tumor response (CR or PR) or SD for at least 24 weeks.

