# 8.6. Disease Response Assessment

Disease response will be assessed by the Investigator, using RECIST v1.1. For both the dose escalation phase (Phase 1) and expansion phase (Phase 2a), imaging results will be collected and preserved for future independent central review, if needed. Tumor assessment with CT and/or MRI will occur at Screening as well as during the last week of Cycles 2, 4, 6, 8, 10, 12 and every 3 cycles thereafter. Partial or CR needs to be confirmed with repeated assessment at least 4 weeks after the initial assessment.

If initial radiological PD is observed, while the clinical condition of the patient is stable, treatment continuation is allowed at the discretion of the Investigator and in consultation with the Sponsor's Medical Monitor. If treatment is continued after initial PD, a confirmatory scan should be acquired

within 4-6 weeks. However, the first successive scheduled timepoint after the confirmatory scan may be skipped if the window is considered not clinically relevant (up to the discretion of the Investigator). The next subsequent timepoint following the skipped timepoint must adhere to the original schedule.

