The ORR (CR or PR), DCR (CR or PR or SD) and CBR (CR or PR or SD ≥24 weeks) assessed by the investigators using RECIST 1.1 will be summarized. The best overall response will be used to define the ORR, DCR and CBR. Best response is defined as the best observed response (CR>PR>SD>PD) throughout the study. See SAP table 1 for rules of response confirmation. Summaries will include the count and percentages and the 95% confidence intervals where appropriate of different best overall responses, ORR, DCR and CBR for each dose level. The percentages will be based on the total number of patients in the Full Analysis Set for a given Expansion Arm.

Waterfall and swimmer plots will also be created, similar to what is described for Phase 1, but additionally color coding of the Best Overall Response.

PK and ADA results matching Phase 1 secondary endpoints will be analyzed, but the presentation will be done by Expansion Cohort rather than by dose level. Analysis of Adverse Events is described in section 8.7.2.

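### Does the unstated start date for 24 weeks of stable disease leave the clinical benefit rate undetermined?

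*Protocol*

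**What the plan says.** The clinical benefit rate (CBR) is a Phase 2a secondary endpoint. Protocol 9.3.2 words it as "Clinical benefit rate (defined as CR or PR [any duration] OR SD ≥24 weeks" and promises a percentage with a 95% CI. Protocol 8.3.2.5 has "overall tumor response (CR or PR) or SD for at least 24 weeks", measured per RECIST v1.1. In SAP 8.6.2 the part reported by Expansion Arm states "CBR (CR or PR or SD ≥24 weeks) assessed by the investigators using RECIST 1.1 will be summarized", and the Phase 1 part uses the same threshold. None of these gives a start date, an end date or a day-count convention for stable disease (SD).

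Scans are due "during the last week of Cycles 2, 4, 6, 8, 10, 12 and every 3 cycles thereafter" (Protocol 8.6). Treatment has two starts: under Protocol 4.2.2, "Seven days prior to Cycle 1 Day 1 (C1D1) (i.e., at Day -7), patients will receive a single dose of AFM24", and the combination and the cycle count begin at C1D1.

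For the time-to-event endpoints, Protocol 8.3.2.2 determines overall survival (OS) by "looking at the time from initial date of treatment to the date of death due to any cause", and Protocol 8.3.2.3 has progression-free survival (PFS) "determined using the time measured from the initial date of treatment". In Protocol 9.3.2, "Progression-free survival will be measured from the date of the first dose of AFM24 and atezolizumab study drug", while OS there starts at the first dose of AFM24 alone.

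**The concern.** A duration threshold needs an origin, and this trial has two natural candidates a week apart. The 24-week mark falls in that week at a scheduled scan. A patient whose SD is last documented at an on-schedule Cycle 6 scan counts as clinical benefit from Day -7 but not from C1D1. In an open-label study with investigator-assessed response, a convention left open could be chosen with results in view. The PFS wording in 9.3.2 adds to the worry: read literally it points to C1D1, whereas the OS sentence in the same section points to Day -7.

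**Working it through.** The documents state no day number for the Cycle 6 scan, so there is no figure of the plan's own to reproduce. The check is calendar arithmetic.

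**Inputs**
- Threshold: 24 weeks = 24 × 7 = 168 days (Protocol 8.3.2.5 and 9.3.2; SAP 8.6.2).
- Cycle length: 28 days, counted from C1D1 (Protocol 4.1 and 4.2.3).
- Scan timing: last week of the cycle, taken as Days 22-28 (Protocol 8.6).
- Lead-in dose: 7 days before C1D1 (Protocol 4.2.2).

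**Formula.** Elapsed days from C1D1 to Day d of Cycle c = (c − 1) × 28 + (d − 1). Add 7 for Day -7. For Cycle 6, Day 22: 5 × 28 + 21 = 161. For Cycle 6, Day 28: 5 × 28 + 27 = 167.

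| Scan | Days from C1D1 | Scan days ≥168 | Days from Day -7 | Scan days ≥168 |
|---|---|---|---|---|
| Cycle 4 | 105-111 | 0 of 7 | 112-118 | 0 of 7 |
| Cycle 6 | 161-167 | 0 of 7 | 168-174 | 7 of 7 |
| Cycle 8 | 217-223 | 7 of 7 | 224-230 | 7 of 7 |

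If both end dates are counted (one day more), C6D28 is day 168 from C1D1. Cycle 6 then gives 1 of 7 from C1D1 against 7 of 7 from Day -7.

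**Visit tolerance (assumed; none is visible).**
- ±3 days: the Cycle 6 scan falls 158-170 days after C1D1, which is 13 dates. Three reach 168 from C1D1 and 10 from Day -7.
- ±7 days: 154-174 days, which is 21 dates. Seven reach 168 from C1D1 and 14 from Day -7.

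The same 7 dates (161-167 days after C1D1) change each time. No Cycle 4 or Cycle 8 date changes: the latest Cycle 4 date from Day -7 is 118 + 7 = 125, and the earliest Cycle 8 date from C1D1 is 217 − 7 = 210. These are counts of calendar dates, not proportions of patients.

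**Who changes status.**
- If SD is timed to the last SD scan, only patients whose last SD scan is at Cycle 6 change. A patient with SD at Cycle 6 and again at Cycle 8 qualifies from either origin.
- If SD is timed to progression, only patients with progression found at the Cycle 6 scan change.
- Patients with a complete or partial response qualify at any duration, so they never change.

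Day -7 only adds days, so it can never give a lower CBR than C1D1. Each patient who changes moves a cohort's CBR by 1/n. The number of such patients cannot be derived from the documents, so neither can the shift in percentage points.

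**PFS and OS.** The PFS phrase in 9.3.2 can mean the first dose of both drugs (C1D1), or it can be a collective name for study drug, as in Protocol 7.2 and 12.2 (Day -7). The difference is 7 days, or 7 / 30.4375 = 0.23 months. OS is not open: 9.3.2 starts it at the first AFM24 dose, which 4.2.1 and 4.2.2 place on Day -7, and the generic wording of 8.3.2.2 is compatible with that.

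**The case for a change.** The strongest case for acting is that the threshold falls at the one scheduled scan where the origin decides the answer. The visible text also uses more than one anchor. SAP 8.2 sets baseline before the first dose of either drug, which is Day -7, while SAP 8.6.2 counts from C1D1 for the waterfall plots. Protocol 4.2.3.1 ties the first combined dose to Cycle 1, which favours reading the PFS phrase as C1D1. Protocol 9.3.2 defers only censoring rules to the SAP, and SAP 8.6.2 describes its Table 1 as covering response confirmation, so the visible text promises no SD-duration rule. The SAP is marked draft and a protocol amendment is announced in SAP section 10, so a sentence now would cost little and would remove a choice otherwise open once results are known.

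The arithmetic and the looseness of the wording stand. That the plan lacks a rule does not. SAP 8.6.1 is almost entirely blank in the public copy, SAP Table 1 is cited but not shown, and the Phase 2a PFS and duration-of-response text cannot be seen. Protocol 8.3.2.5 also refers to RECIST v1.1, whose text was not available here. Nor does the objection show that any stated rule or number is wrong. It asks for one of two origins to be named without a reason to prefer either.

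**Conclusion.** No change to the plan is needed. The gap is real in the visible wording but narrow: one scheduled scan, and among patients with SD only those whose last SD scan or progression is at that scan. CBR is a secondary endpoint, SAP 8.1 makes the analyses descriptive unless otherwise stated, and no visible decision rule uses CBR. The primary objective response rate does not depend on the origin. For PFS the choice shifts times by 7 days and changes no visible decision; OS is already anchored at Day -7.

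Either origin gives a sound endpoint. The full analysis set requires some of both drugs, so every patient in it has both dates and nothing is lost whichever is used. An analyst would name the origin and end date when deriving SD duration and report them with the result. The one substantive alternative, counting an on-schedule Cycle 6 scan as 24 weeks when C1D1 is the origin, would accept 161-167 days (about 23-24 weeks). That relaxes the stated threshold, so it is a trade-off and not a correction.

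This conclusion rests on the nominal scan schedule, on elapsed-day counting except where noted, and on the visible text alone. If the SAP text not shown here already fixes the convention, even the clarification falls away.

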#### 9.3.3. Pharmacokinetic Analyses

The PK analysis plan for the assessment of AFM24 will be described in a separate Data Analysis Plan. Where feasible, non-compartmental analysis will be conducted using concentration time data of AFM24. Summary statistics of PK parameters such as  $C_{max}$ , time to  $C_{max}$  ( $T_{max}$ ),  $C_{min}$ , and area under the concentration-time curve over the dose interval (AUCtau) will be reported by dose group. Additional parameters or model-based analysis may be calculated depending on the available data.

In the expansion cohorts, owing to sparse data sampling population exploratory PK analysis may be conducted to provide more comprehensive PK parameters for these patients. If a population PK analysis is conducted, all available clinical PK data from AFM24 will be used.

## 9.3.4. Other Analyses

## 9.3.4.1. Demographics, Medical History, Prior Medication and Other Baseline Characteristics

Demographic characteristics, prior anti-cancer therapies and surgeries, medical history, prior medication, and other baseline data will be listed and summarized using descriptive statistics for numerical data and contingency tables for categorical data. Medical history and prior medication will be listed. Prior anti-cancer therapies will be coded by World Health Organization (WHO) Anatomical, Therapeutic and Chemical (ATC) terms and summarized. Prior cancer surgeries will be summarized.

#### 9.3.4.2. Study Treatment

Exposure to AFM24 will be summarized with descriptive statistics for the total number of infusions received. The total amount of time on AFM24 (duration of dosing in weeks) and atezolizumab will also be derived and summarized. The number of infusions with interruptions (regardless of reason) will be summarized by dose cohorts and total.

[figure not shown]
#### 9.3.4.3. Concomitant Medication

Concomitant medication, especially mandatory pre-medication, and significant non-drug therapies after the start of study treatment will be listed and summarized by WHO ATC term in contingency tables.

#### 9.3.4.4. Immunogenicity

Immunogenicity parameters will be summarized by descriptive statistics and listed.

Affimed GmbH Protocol Confidential

#### 10. SAFETY MANAGEMENT

Timely and complete reporting of safety information is very important to assist in the identification of any untoward medical occurrence, thereby ensuring:

- The safety of study patients;
- A greater understanding of the overall safety profile of the investigational drug;
- Recognition of any dose-related investigational drug toxicity;
- Appropriate modification of study protocols;
- Improvements in study design or procedures as required; and
- Adherence to required ethical and regulatory requirements for clinical study conduct.

## **10.1.** Safety Definitions

#### 10.1.1. Adverse Events

An AE is defined as any new untoward medical occurrence or worsening of a pre-existing medical condition in a patient or clinical investigation patient administered a medicinal product and which does not necessarily have a causal relationship with this treatment. An AE can therefore be any unfavorable and unintended sign (including a clinically significant abnormal laboratory finding, for example), symptom, or disease temporally associated with the use of a medicinal (investigational) product or study procedures, whether assessed as related or unrelated to AFM24.

During clinical trials, AEs can be spontaneously reported or elicited during open-ended questioning, examination, or evaluation of a patient. To prevent reporting bias, patients should not be questioned regarding the specific occurrence of one or more AEs. Adverse events include:

- Worsening (change in nature, severity, or frequency) of conditions present at the start of the study;
- Intercurrent illness;
- Drug interactions;
- Experiences related or possibly related to concomitant medications;
- Clinically significant abnormal laboratory values or shifts from baseline;
- Clinically significant abnormalities in physical examination, vital signs, weight, or ECG; and
- An accident or injury;
- Adverse events which are related to study procedures (for example: a biopsy).

